9.2.1 Study Period

The planned period for data collection will be approximately 2 years. However, as the timing of product launch and the time needed for regulatory/ethics approval will vary between countries, the exact length of this period is expected to differ between countries. The study will commence at an appropriate time post-launch in each participating country to allow for reasonable uptake of the product and familiarisation and use of the materials by HCPs.

9.2.2 **Selection and Number of Sites**

HCPs working at sites in which the OBI is being prescribed or expected to be prescribed will be approached for participation in the study. In order to rapidly recruit respondents, sites are likely to be selected based on volume of historical Neulasta and observed OBI use (ie, sales data) from six months after product launch in the country. To facilitate the representativeness of the sample, up to three HCPs per site will be participating in the study, and up to 9 patients will be allowed to be included per site.

Based on expected average site level use of the OBI, it is estimated that approximately 20 sites will need to be included in the study to recruit 80 new respondents into the study in 2 years. Assuming a site participation rate ranging 10-15%, to include 20 sites, would

Date: 10 April 2019 Page 20 of 61

require contacting approximately 133 – 200 sites for participation. If the site participation rate is < 10% after 50 sites have been asked to participate, Amgen will re-assess study methods for the probability of achieving study objectives successfully.

The number of HCPs contacted but not participating in the study will be recorded and their characteristics (ie, gender, age, years of practice and size/type of practice) will be gathered where possible to assess potential selection bias.

9.2.3 Subject Eligibility

Product: Peafilarastim

9.2.3.1 **Inclusion Criteria**

- Respondent (ie, patients or caregivers primarily responsible for monitoring the OBI) who agrees to be contacted for the questionnaire.
- Respondent aged 18 or more years.
- Respondent with no cognitive impairment.
- Respondent who can read and understand the language in which the study is being conducted and in which the PAC is provided.
- Patient has been prescribed the OBI for Neulasta delivery for their current chemotherapy cycle.
- Patient and respondent provide their written informed consent to participate in the study.

Respondents can be included in the study regardless of the number of times they have monitored the OBI previously

9.2.3.2 **Exclusion Criteria**

- Respondent personally works, or works on a consultancy basis, for any pharmaceutical company or advertising/research agency.
- Patient has participated or is participating in a clinical trial of Neulasta administered via OBI.

9.2.4 Matching

Not Applicable.

9.2.5 **Baseline Period**

This is a cross-sectional study that does not involve any follow-up of respondents. Eligibility criteria will be assessed on the date of OBI administration and the respondent questionnaire will be administered approximately 27 to 72 hours after the OBI application (ie, approximately 0 to 45 hours after the Neulasta dose is expected to be delivered through the OBI). Respondents can be included in the study multiple times at different chemotherapy cycles in which the OBI is being prescribed to the patient, if eligibility criteria including informed consent are met (Section 9.2.3). In subsequent applications

Date: 10 April 2019 Page 21 of 61

of the questionnaire, data will only be collected to meet the primary objective regarding medication errors. This administration of the questionnaire will be considered independent from the previous one and no follow-up period will be considered.

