7.3 Statistical Inference (Estimation or Hypothesis)

This is an estimation study. Due to sample size limitations, no formal hypothesis will be tested. Results will be presented as estimates with 95% confidence intervals as measures of precision.

8. Research Question and Objectives

The study aims to address the following research questions:

- Has the implementation of the PAC as an aRMM been conducted as planned?
- What is the level of respondent awareness and behavioural intent to act as recommended in the PAC?
- What is the rate of medication errors observed in routine clinical practice?

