9.5 Study Size

This study aims to include approximately 80 respondents, however, the final sample size will ultimately depend on the uptake of the OBI in participating countries and willingness of respondents to participate. Expected OBI use in Europe is <10,000 patients per year, therefore, a sample size of 80 respondents is considered feasible.

Table 2 gives the 95% confidence interval half-width around the proportion of respondents with correct answers to the questions around awareness and behavioural intent for a given sample size of questionnaire respondents.

Table 2. Half-width of 95% Confidence Intervals for Different Proportions of Correct Answers to Questions by Size of Questionnaire Respondents

Sample Size	Proportion	Half-width 95% CI
60	0.5	0.13
60	0.6	0.12
60	0.7	0.12
60	0.8	0.10
60	0.9	0.08
80	0.5	0.11
80	0.6	0.11
80	0.7	0.10
80	0.8	0.09
80	0.9	0.07
100	0.5	0.10
100	0.6	0.10
100	0.7	0.09
100	0.8	0.08
100	0.9	0.06

95% CI calculated using the normal approximation

Date: 10 April 2019 Page 25 of 61

Assuming patients will use the OBI on average 3.5 times during a single chemotherapy course, 80 independent patients are estimated to receive a maximum of 280 OBI applications.

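### Repeat applications are declared independent although several per patient enter the medication-error proportion, and, separately, Table 2 allows nothing for clustering by site

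*Protocol*

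**What the plan says.** **Repeat applications.** A respondent may enter again at later chemotherapy cycles, and the partial questionnaire then collects medication-error data only (Protocol 9.1, 9.2.5, 9.3). Section 9.2.5 states: "This administration of the questionnaire will be considered independent from the previous one". Section 9.7.1 puts every reported application into the medication-error sample and allows several per respondent. Section 9.7.2.4 presents errors per administration as well as per subject. It looks at initial and subsequent applications separately and pools them if no difference is seen. Section 9.5 expects that "80 independent patients are estimated to receive a maximum of 280 OBI applications". Section 9.7.2.5 plans no sensitivity analysis.

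**Precision of the respondent-level results.** Section 7.3 makes this an estimation study: "Results will be presented as estimates with 95% confidence intervals as measures of precision". Table 2 in section 9.5 gives the "95% confidence interval half-width around the proportion of respondents with correct answers to the questions around awareness and behavioural intent", with the footnote "95% CI calculated using the normal approximation". Section 9.2.2 plans about 20 sites for 80 respondents and says "up to three HCPs per site will be participating in the study, and up to 9 patients will be allowed to be included per site". Table 1 in section 9.3.2 reads both success measures from whether 70% falls inside the 95% CI. The PAC-success measure is confined to respondents who received the card.

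**The concern.** These are two separate problems.

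1. Applications to the same patient share the patient, usually the respondent and often the HCP, so they are repeated measures. If the sentence in 9.2.5 is carried into the analysis, the per-administration CI uses the wrong variance. The medication-error estimate answers one of the study's three research questions, and its interval is the only statement of uncertainty about it.

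2. The PAC reaches respondents through HCPs (sections 4 and 7.1), and section 9.9.2 concedes that HCPs may change how they distribute it because they are in the study. Section 9.7.2.4 itself describes the composite score by HCP and site. Receipt and knowledge may therefore be alike within a site, yet Table 2 treats respondents as unrelated. Table 2 also counts all questionnaire respondents, whereas the PAC-success measure counts recipients only. Because both success measures are read from the CI, its width bears directly on the stated outcome.

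**Working it through.** **Inputs from the protocol.** n = 80 respondents; about 20 sites, so 80/20 = 4 per site, with a cap of 9 (9.2.2); 3.5 applications per patient on average (9.5); 5 unsuccessful administrations in 297 = 1.7% in the healthy-subject device study (7.1), used only as an illustration. **Assumed, because the protocol gives none:** patient ICC 0.1 to 0.3, site ICC 0.05 to 0.2, equal cluster sizes. Unequal sizes would raise the design effects.

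**Reproducing the plan's figures.** Half-width = 1.96 × √(p(1−p)/n). At n = 80, p = 0.7: 1.96 × √(0.21/80) = 0.1004, stated as 0.10. All 15 cells of Table 2 match this formula to two decimals, so the table carries a design effect of exactly 1. Also 80 × 3.5 = 280. This is 80 times an average, hence an expectation rather than a maximum.

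**Point 1: repeat applications.** Design effect DE = 1 + (3.5 − 1) × ICC; effective n = 280/DE; the interval must widen by √DE.

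| Patient ICC (assumed) | DE | Effective n | Widening | Coverage of naive 95% CI | Half-width at 1.7% | Half-width at 5% |
|---|---|---|---|---|---|---|
| 0 | 1.00 | 280 | 1.00 | 95% | 1.5 points | 2.6 points |
| 0.1 | 1.25 | 224 | 1.12 | 92% | 1.7 | 2.9 |
| 0.2 | 1.50 | 187 | 1.22 | 89% | 1.9 | 3.1 |
| 0.3 | 1.75 | 160 | 1.32 | 86% | 2.0 | 3.4 |

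The half-widths only show scale. Coverage is the large-sample value for an otherwise correct interval.

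Reporting initial and subsequent applications apart removes only part of this. The subsequent group would hold 280 − 80 = 200 applications, 200/80 = 2.5 per patient, with DE = 1 + 1.5 × ICC = 1.15, 1.30 and 1.45 at the same ICCs.

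**Point 2: sites in Table 2.** For a binary result measured once per respondent (PAC receipt, or one question), DE = 1 + (m − 1) × ICC, and the half-width at n = 80, p = 0.7 is 0.1004 × √DE.

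| Site ICC (assumed) | DE, m = 4 | Half-width, m = 4 | Half-width if every site reached 9 |
|---|---|---|---|
| 0.05 | 1.15 | 0.108 | 0.119 |
| 0.1 | 1.30 | 0.114 | 0.135 |
| 0.2 | 1.60 | 0.127 | 0.162 |

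**Recipients only.** At an assumed 70% receipt, n = 0.7 × 80 = 56. For a single question at p = 0.7 the half-width is 1.96 × √(0.21/56) = 0.120 before clustering. With 56/20 = 2.8 recipients per site and ICC 0.2, DE = 1 + 1.8 × 0.2 = 1.36, giving 0.120 × √1.36 = 0.140.

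**Composite score.** Each respondent's score lies between 0 and 1, so its variance cannot exceed p(1−p). With an assumed SD of 0.25 the half-width at n = 80 is 1.96 × 0.25/√80 = 0.055. Even at a design effect of 2.5 it is 0.055 × √2.5 = 0.087, below the tabulated 0.10.

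**Effect on Table 1.** Suppose 47 of 80 report receipt (58.75%). The simple half-width is 1.96 × √(0.5875 × 0.4125/80) = 0.108, so the upper limit is 0.695 and 70% lies outside. At site ICC 0.05 the half-width is 0.108 × √1.15 = 0.116, the upper limit is 0.703 and 70% lies inside. Under the literal rule the wider interval turns failure into success.

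**The case against.** The strongest reply is that the sentence in 9.2.5 stands under the baseline period and explains why a cross-sectional study has no follow-up; it need not be a variance assumption. The analysis sections never say that intervals assume independence, no CI method is fixed for medication errors, and the SAP may supply one. Section 9.7.2.4 also plans subject-level proportions, which largely avoid the repeat-measures problem. This is fair, and it limits the weight of point 1. It does not remove it: the sentence is unqualified, the only data it can apply to are the medication-error data, and nothing else in the protocol mentions within-patient correlation.

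On Table 2, the n = 60 row already shows 0.12 at p = 0.7. That is about the half-width for 56 recipients, and it covers a site ICC of 0.1 at n = 80. So the table spans part of the shortfall, but it presents that row as a smaller sample, not as an allowance for clustering or for recipients.

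Four stronger readings are tempting, and the documents do not support them:

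- *That repeat applications make Table 2 or the primary result too precise.* Awareness and intent are assessed at the first monitored application only (sections 4 and 9.7.1), and Table 2 covers only those questions.
- *That rare medication errors will get a normal-approximation interval.* The footnote belongs to Table 2, whose proportions run from 0.5 to 0.9. The protocol fixes no interval for errors and states no precision for them beyond the count of 280.
- *That the stated 0.10 is shown to be too small for the composite score.* It may be conservative there before clustering.
- *That clustered intervals would make the success criterion stricter.* The 47-of-80 example shows the opposite.

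**Conclusion.** Both points hold in a limited form. First, the independence statement in 9.2.5 should not govern the per-administration medication-error CI. If it does, that CI is too narrow for any positive within-patient correlation, by a factor of 1.12 to 1.32 at assumed ICCs of 0.1 to 0.3. Second, Table 2 has no allowance for sites. For PAC receipt and single questions the understatement is slight at a site ICC of 0.05 (0.108 against 0.10) and moderate at 0.1 to 0.2 (0.114 to 0.127). The direction is sure for any positive correlation; the size rests wholly on assumed ICCs and on equal cluster sizes. Calling 280 a maximum is a minor wording error. The matter should be corrected, but it does not undermine the design or the sample size.

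**What to change.** 1. In section 9.2.5, delete the independence wording or limit it to eligibility and follow-up. State that the 95% CI for the per-administration medication-error proportion uses a variance clustered by patient, or by site (which contains patients), with a small-sample correction. With about 20 sites that means about 20 − 1 = 19 degrees of freedom for site clustering. Cluster on patient rather than respondent, since 9.1 lets a patient's respondent change. The codes in 9.6.2 already allow this. Keep the patient-level proportion as planned.
2. In section 9.5, add to Table 2 a range of design effects with the assumed site ICCs, and a row for PAC recipients (for example n = 56). Note that the table describes single binary items and that the composite score may be estimated more precisely.
3. State that the CIs for PAC receipt and the composite score are clustered by site.
4. Where Table 1 is discussed, do not present the wider intervals as a stricter test; say that under the literal rule they make it easier for 70% to fall inside.
5. Describe 280 as the approximate number expected if all applications are captured.

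The cost is protocol and SAP wording and a slightly less favourable precision table. No extra patients or data items are needed.

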9.2.6 Study Follow-up

No follow-up is conducted after the questionnaire administration in this cross-sectional study.

9.3 Variables

Variables collected in the respondent questionnaire, to be administered approximately 27 to 72 hours after OBI application, will include:

- Respondent demographics and characteristics, including age, sex, educational level, self-reported language skills, self-reported confidence to monitor the OBI, health literacy - using the questions from the Brief Health Literacy Screen (BHLS) questionnaire (Chew et al. 2004) -, respondent type (patient or caregiver)
- Respondent prior use and/or monitorisation of the Neulasta OBI
- Details of respondent receipt and use of the PAC
- Respondent reported awareness of key safety messages in the PAC (eg, OBI alerts for Neulasta dose delivery or issues, time of removal of OBI, etc.)
- Respondent reported behavioural intent to carry out recommended actions as described in the PAC (eg, symptoms related to infection, issues with Neulasta dose delivery via the OBI, etc.)
- Device issues experienced by the patient (eg, whether the device came loose, red light came on, leakage, etc.) and any resulting actions*
- Symptoms of adverse events potentially related to medication errors experienced by the patient (eg, fever, chills, sweating, etc.) and related consultations with HCPs*
- Details on dose delivery (eg, expected dose delivered on time, partial dose received, etc.)*
- Occurrence of a replacement G-CSF dose (eg, type of replacement and timing)*

In addition, the HCP will report the following variables through an eCRF, to be completed at the time of respondent identification and consent:

- HCP and site characteristics (only reported once per HCP)
- HCP awareness of methods to obtain the PAC
- Date and time of OBI application
- Device issues observed by the HCP at the time of OBI application (eg, the device coming loose, problems filling the device, leakage, etc.)

^{*} Indicates variables to be collected in the partial respondent questionnaire

Date: 10 April 2019 Page 22 of 61

9.3.1 **Exposure Assessment**

Product: Pegfilgrastim

Patients included in the study will have been administered the OBI as per routine clinical practice.

9.3.2 **Outcome Assessment**

The primary endpoint for the respondent questionnaire is:

Awareness of key safety messages and behavioural intent to carry out recommended actions as described in the PAC: will be evaluated using a set of multiple choice questions included in the questionnaire. A composite score for each individual will be calculated based on the proportion of all awareness and behavioural intent questions with correct responses.

The secondary endpoints for the respondent questionnaire are:

- Receipt of the PAC by the respondent: a categorical variable will describe if the respondent received the PAC.
- Medication errors with OBI administrations. The proportion of total OBI administrations with medication errors with respect to total OBI administrations, and the total number of patients will be calculated.

Measure of Success

The results of the study will be interpreted considering an acceptable level of patients and/or caregivers awareness and behavioural intent. The study estimates and associated 95% confidence intervals (CIs) will be evaluated in the context of a desired population-level threshold of at least 70%. The selection of a threshold for success is subjective and not based on a priori knowledge, experience, or established scientific criteria in the education or risk communication or evaluation literature. Therefore, the results will be contextualised with other available information. The appropriateness of the minimum 70% threshold as a measure of success will be reviewed at the time of the 1-year interim analysis.

Table 1. Measures of Success

Description of measure	Assessment
Distribution of the PAC	The threshold of 70% is within the 95% CIs of the proportion of respondents who provide an affirmative response to the key question regarding receipt of the PAC.
Success of the PAC	For the respondents who have received the PAC, the threshold of 70% is within the 95% CIs of the composite score for awareness and behavioural intent

Date: 10 April 2019 Page 23 of 61

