9.7.1.1 Interim Analysis/Analyses

An interim analysis is planned to be implemented at 1 year after start of data collection. All respondents and OBI applications available at time of analysis will be included. All descriptive tables planned for the final analysis will be also performed in the interim analysis. The appropriateness of the minimum 70% population-level threshold established as the measure of success for the distribution of the PAC and for the awarereness and behavioural intent to carry out recommended actions in the PAC will be reviewed at the time of the 1-year interim analysis, and addressed if required.

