9.7.2.4 Analysis of the Primary, Secondary and Exploratory Endpoint(s) Primary

Awareness of key safety messages and behavioural intent to carry out recommended actions will be analysed considering individual questions, as well as calculating a composite score. The composite score will be calculated based on the proportion of all awareness and behavioural intent questions with correct responses. Composite scores will be described using descriptive measures for continuous variables, as well as categorical variables using a cut-off point of 70% of correct responses. The composite score will also be presented by whether the respondent received the PAC or not (if occurred), by prior OBI administrations and by the level of health literacy. Awareness and behavioural intent of respondents (composite score) will be also described at

Date: 10 April 2019 Page 31 of 61

HCP/site level and analysed according to site and HCP professional characteristics and prior experience with Neulasta OBI. The primary objective will be analysed in the full sample of respondents who fulfill selection criteria (full analysis set of respondents).

Secondary

In order to assess if the respondent received the PAC, the unique specific question included in the questionnaire will be used. The number and percentage of respondents who have received the PAC will be reported.

This study will help indicate if the PAC is effective as an aRMM based on the assessment described in Section 9.3.2. For the respondents who have received the PAC, the composite score and associated 95% CIs for awareness and behavioural intent will be reported. The selection of a threshold for success is subjective and not based on a priori knowledge, experience, or established scientific criteria in the education or risk communication or evaluation literature. Therefore, the results will be contextualised with other available information.

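### Table 1 counts a result as a success only if 70% lies inside its 95% CI, so results well above 70% fail and results below 70% can pass

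*Protocol*

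**What the plan says.** Under *Measure of Success*, Protocol Section 9.3.2 says the estimates and their 95% CIs will be judged "in the context of a desired population-level threshold of at least 70" per cent. Section 9.7.1.1 repeats the one-directional wording: "The appropriateness of the minimum 70% population-level threshold established as the measure of success for the distribution of the PAC" is to be reviewed at the interim analysis.

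Table 1 in Section 9.3.2 then defines the two measures:

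- Distribution of the PAC: "The threshold of 70% is within the 95% CIs of the proportion of respondents who provide an affirmative response" to the question on receipt.
- Success of the PAC, among recipients: "the threshold of 70% is within the 95% CIs of the composite score for awareness and behavioural intent".

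Section 9.7.2.4 says the study will indicate whether the PAC is effective on the basis of the assessment in Section 9.3.2. It summarises the composite score as a continuous variable, "as well as categorical variables using a cut-off point of 70% of correct responses". The protocol nowhere says that an interval lying wholly above 70% also counts as success.

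**The concern.** A minimum has one direction, whereas lying inside an interval has two sides. Read literally, Table 1 has three consequences:

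1. A result whose whole interval is above 70% is not a success.
2. A result below 70% is a success as long as its upper limit reaches 70%.
3. Because the interval widens as the sample shrinks, the range of passing results grows when less information is collected.

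Table 1 is the only success criterion the protocol states for PAC distribution (a secondary objective) and for PAC effectiveness. The final report goes to PRAC, so a verdict that runs against the data would reach the regulator.

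There is also a smaller uncertainty in the composite row. It does not say whether the interval is for the mean score or for the share of respondents scoring at least 70%, although Section 9.7.2.4 plans both summaries.

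**Working it through.** **Inputs.** The success rule comes from Table 1 and the 95% level from Section 7.3. Section 9.5 gives n = 80, the planning grid of 60, 80 and 100, and the normal-approximation interval (note under Table 2). The protocol gives no SD for the composite score; 10 to 25 percentage points is assumed here.

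**Reproducing Table 2.** Half-width = 1.96 × √(p(1−p)/n).

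- n = 80, p = 0.7: 1.96 × √(0.21/80) = 0.100 (Table 2: 0.10)
- n = 80, p = 0.9: 1.96 × √(0.09/80) = 0.066 (Table 2: 0.07)

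All 15 cells agree to two decimals.

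**Applying Table 1 to observed receipt at n = 80.**

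| Positives | Estimate | 95% CI | 70% inside? |
|---|---|---|---|
| 47 | 58.8% | 48.0% to 69.5% | no |
| 48 | 60.0% | 49.3% to 70.7% | yes: success |
| 63 | 78.8% | 69.8% to 87.7% | yes: success |
| 64 | 80.0% | 71.2% to 88.8% | no: not success |
| 72 | 90.0% | 83.4% to 96.6% | no: not success |

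The passing set is therefore 48 to 63. With Wilson or exact (Clopper-Pearson) intervals it is 48 to 64, so the interval method is not the cause.

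**Probability of success at n = 80.** This is the sum of Binomial(80, p) over x = 48 to 63.

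| True receipt | 60% | 65% | 70% | 75% | 80% | 85% | 90% |
|---|---|---|---|---|---|---|---|
| P(success) | 54.8% | 85.1% | 94.9% | 81.5% | 43.4% | 8.4% | 0.2% |

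The probability peaks at about 70% and falls on both sides. A programme that truly reaches 60% is more likely to succeed than one that reaches 80%.

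**Effect of sample size (same interval method).**

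| n | Passing range | P(success), true 60% | P(success), true 90% |
|---|---|---|---|
| 20 | 50% to 85% | 86.9% | 32.3% |
| 60 | 58.3% to 80% | 65.6% | 1.5% |
| 80 | 60% to 78.8% | 54.8% | 0.2% |
| 100 | 61% to 78% | 46.2% | <0.1% |

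At a true value of exactly 70% the probability stays near 95% at every n. The advantage of less data arises for true values away from 70%.

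**Composite row read as a mean score, n = 80.** Half-width = t(79) × SD/√80, with t(79) = 1.990 and √80 = 8.944.

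- SD 10: 1.990 × 10/8.944 = 2.2 points; passing means 67.8% to 72.2%
- SD 20: 1.990 × 20/8.944 = 4.5 points; passing means 65.5% to 74.5%
- SD 25: 1.990 × 25/8.944 = 5.6 points; passing means 64.4% to 75.6%

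An observed mean of 80% fails in all three cases.

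**The case against.** The strongest reply has four parts.

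- **The intent is clear.** The paragraph above Table 1 says at least 70%, so a sensible reader would treat an interval wholly above 70% as success, and the table cell is only badly worded. That is probably the intent, but the table is where success is defined and nothing in the protocol overrides it. Knowing the direction also does not settle the rule. At n = 80, requiring the upper limit, the point estimate or the lower limit to reach 70% needs 48, 56 or 64 positives respectively (65 for the lower limit with an exact interval).
- **Leniency may be deliberate.** Section 7.3 disclaims hypothesis testing: "Results will be presented as estimates with 95% confidence intervals as measures of precision". Accepting a result still compatible with 70% is a defensible choice in a small study. This carries some weight for the lower side, but it does not explain why a clearly better result should fail. The caveats about a subjective threshold, contextualised results and interim review concern the figure of 70%, not the inside-the-interval rule.
- **The sample-size effect is limited.** It vanishes at a true 70%, and n = 20 lies outside the planning grid. Both points are right. Within 60 to 100 the probability at a true 60% still falls from 65.6% to 46.2% as n grows. Section 9.5 also leaves the size open: "This study aims to include approximately 80 respondents, however, the final sample size will ultimately depend on the uptake of the OBI". The composite row uses PAC recipients only, so its n may be smaller still.
- **The composite row naturally means the mean score.** This is the likelier reading, since Section 9.7.2.1 gives a mean and 95% CI for continuous outcomes. The ambiguity is minor, and one phrase would remove it.

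**Conclusion.** Table 1 is wrong as written: both rows contradict the minimum of 70% set in the same section and repeated in Section 9.7.1.1. For distribution at n = 80, success is confined to 60.0% to 78.8% observed receipt, and its probability falls from 94.9% at a true 70% to 0.2% at a true 90%, while a true 60% succeeds 54.8% of the time. These figures assume independent respondents and the Table 2 interval; Wilson and exact intervals move only the upper edge, by one respondent. The composite figures rest on an assumed SD of 10 to 25 points and on all 80 respondents having received the card, but an observed mean of 80% fails across that whole range. Because the error sits in the definition of success and can reverse the verdict, it must be fixed before the data are seen.

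**What to change.** Replace both cells of Table 1 with a one-directional rule:

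- **Met:** the point estimate is at least 70%.
- **Demonstrated:** the lower 95% limit is also at least 70%.
- **Not met:** the upper 95% limit is below 70%.
- **Inconclusive:** anything else, that is, an estimate below 70% with an upper limit of 70% or more.

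State the interval method for the receipt proportion. In the composite row, specify the mean composite score of PAC recipients and keep the share scoring at least 70% as description only. The labels classify estimates and need no hypothesis test.

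For receipt at n = 80 with an exact interval, the rule gives: not met at 47 or fewer, inconclusive at 48 to 55, met at 56 to 64, and demonstrated at 65 or more. The probability of an estimate of at least 70% (56 or more) is then 20.7%, 55.5% and 98.9% at a true 65%, 70% and 80%. The probability of *demonstrated* is 1.6%, 45.5% and 99.5% at a true 70%, 80% and 90%. Both rise with true performance, as a minimum requires.

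The cost is a wording change in Table 1 with matching SAP text, made by protocol amendment with the ethics approval that Section 12.1 requires. No extra data are needed. The sponsor has to accept that *demonstrated* receipt needs 65/80 (81%) at the planned size. For the composite mean at n = 80 it needs 70% plus the half-width, which is 72.2% to 75.6% over the assumed SDs.
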